### ***6.3.2. Missing COVID-19 Status or Disease Severity***

For the primary and key secondary endpoints, if a participant has at least one post-baseline RT-PCR test result and has not yet met the criterial for COVID-19 or is missing data used to determine COVID-19 status, the participant will be treated as not experiencing COVID-19. The same logic will be used for moderate-or-worse severity COVID-19.

As a supplementary analysis on these endpoints, the approach described in Section [6.3.1](#) will be used to handle missing COVID-19 status or disease severity due to death unrelated to COVID-19, study discontinuation, or the triggering of the Primary Database Lock. Participants with missing information will be treated as not experiencing the associated endpoint event and will be weighted based on the proportion of the Evaluation Period that was completed.

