Vital signs	X	Daily										X	X	X		Documentation of hospital-based exam is acceptable. Includes: body temperature, pulse rate, BP, SpO ₂ , respiratory rate, FiO ₂ if known, and method of delivery, if applicable. Record while participant is at rest.

Procedures	Screening	Evaluation Period										ETV	Post-Evaluation Follow-Up			Comments
Study Day	Max 7-day window	1	2-7	8	15	22	29	36	43	50	57		85	141	169	
Visit window (\pm number of days)	--	--	--	2	2	2	2	2	2	2	2		7	7	7	
Hospitalization events		Daily										X	X	X		Record if the following events occur: 
Emergency room visitshospitalizedICU admittance,Extended care facility admittance,and discharge for any of the above
Clinical status and concomitant procedures of special interest in hospitalized participants		Daily										X	X	X		Documentation from hospital records is acceptable. Includes: consciousness status (ACVPU), limitation on activities due to COVID-19, and requirements for 
Ongoing hospital medical careSupplemental oxygennon-invasive ventilation or a high flow oxygen devicemechanical ventilationextracorporeal membrane oxygenation, oradditional organ support (e.g. pressors, renal replacement)
Clinical symptoms and interventions of interest		Daily										X	X			See Table 1 for clinical symptoms and interventions of interest.

Procedures	Screening	Evaluation Period										ETV	Post-Evaluation Follow-Up			Comments
Study Day	Max 7-day window	1	2-7	8	15	22	29	36	43	50	57		85	141	169	
Visit window (\pm number of days)	--	--	--	2	2	2	2	2	2	2	2		7	7	7	
Symptoms Questionnaire	X	Daily										X	X		See Section 8.1.2.	
SARS-CoV-2 POC Test (Nasal Swab)	X														Applies to participants in Part 2 only. Result must be determined prior to collecting swabs for PCR test.	
SARS-CoV-2 Serology		X				X			X	X	X	X	X	X	Day 1: pre-dose. assessed at a central laboratory	
SARS-CoV-2 nasopharyngeal swab (for PCR test) taken from both nostrils		X													Day 1: pre-dose. assessed at a central laboratory	
SARS-CoV-2 nasal swab (for PCR test) taken from both nostrils		X		X	X	X	X	X	X	X	X	X	X		Day 1: pre-dose. assessed at a central laboratory No samples needed if participant is hospitalized.*	

Procedures	Screening	Evaluation Period										ETV	Post-Evaluation Follow-Up			Comments
Study Day	Max 7-day window	1	2-7	8	15	22	29	36	43	50	57		85	141	169	
Visit window (\pm number of days)	--	--	--	2	2	2	2	2	2	2	2		7	7	7	

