The maximum total duration of study participation for each participant of the treatment group is 12 weeks. See the SOA for the treatment group in Section 1.3.2.

This table describes the visit types for the prevention population for this study.

Study Day	Activity	Visit Type
0,1	Follow SoA	Onsite
8, 15, 22, 29, 36, 43, 50, 57	Follow SoA Vital signs*	Onsite or Home (Virtual [record collection] if hospitalized)

Daily 2 - 57	Vital signs and symptoms questionnaire daily* Vital signs, clinical status, and concomitant procedures for hospitalized participants.	Onsite or Home (Virtual [record collection] if hospitalized)
ETV and follow-up (85, 141, 169)	Follow SoA	Onsite or Home

*Collected via direct data capture for onsite or home visits only.

This table describes the visit types for the treatment population for this study.

Study Day	Activity	Visit Type
0, 1	Follow SoA	Onsite
8, 29	Follow SoA Vital signs*	Onsite or Home (Virtual [record collection] if hospitalized)
Daily 2-29	Vital signs, clinical status, and concomitant procedures for hospitalized participants.	Virtual (record collection) if hospitalized
ETV and follow-up (85)	Follow SoA	Onsite or Home

*Collected via direct data capture for onsite or home visits only.

Hospitalization

If a participant is hospitalized, efforts will be made to retrieve hospital records and report procedures and assessments according to the SoA, as feasible.

Definitions for COVID-19 Severity

This table gives the definitions for COVID-19 severity of illness for those participants who are SARS-CoV-2 positive as determined by standard RT-PCR assay or equivalent test.

Table 1 Definitions for COVID-19 Severity

Severity	Description
Mild	Mild symptoms that could include: 
 fever, cough, sore throat, malaise, headache, muscle pain, gastrointestinal symptoms, without shortness of breath or dyspnea AND No clinical signs indicative of Moderate, Severe, or Critical Severity
Moderate	Symptoms of moderate illness with COVID-19, which could include any symptom of mild illness or shortness of breath with exertion AND Clinical signs suggestive of moderate illness with COVID-19, such as: 
 respiratory rate \geq 20 breaths per minute,

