### ***6.3.1. Missing SARS-CoV-2 Infection Status***

For the primary and key secondary endpoints, participants in the Prevention population with zero post-baseline RT-PCR test results will be excluded. If a participant has at least one post-baseline RT-PCR test result and has not yet tested positive or is missing additional test results during the time frame of the endpoint, the participant will be treated as SARS-CoV-2 negative at all visits before the last available RT-PCR test, and will be treated as not experiencing the event of interest in the primary and key secondary analyses.

As a supplementary analysis on the key secondary endpoint for incidence of SARS-CoV-2 infection, weights equal to the proportion of the Evaluation Period completed will be used in the logistic regression analysis. If a participant has a missing SARS-CoV-2 Infection Status due to death, study discontinuation, or the triggering of the Primary Database Lock, the participant will be treated as SARS-CoV-2 negative with a weight equal to the proportion of the Evaluation Period (up to Day 29) completed prior to the discontinuation event or the Database Lock.

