## 6.10. Efficacy Analyses

### 6.10.1. Primary Outcome and Methodology

The endpoint for the primary analysis is defined as the first occurrence of COVID-19, defined as the detection of SARS-CoV-2 by reverse transcription – polymerase chain reaction (RT-PCR) AND mild or worse disease severity within 21 days of detection, by Day 57 (8 weeks after randomization).

The percentage of patients in the Prevention population who experience COVID-19 by Day 57 will be summarized by treatment group.

Statistical comparison between each study intervention and placebo will be done using a logistic regression model. The model will include treatment, facility, role within the facility (resident vs staff) and sex as fixed effects. The odds ratio and the corresponding CIs, as well as the treatment differences and the corresponding CIs, will be computed using the Wald method and reported. A p-value from the Rao's score test will be reported.

As an exploratory analysis, the incidence of COVID-19 within 21 days of randomization will be compared across treatment groups in the subset of participants in the Treatment population who are asymptomatic at baseline (as defined in Table 1 of the protocol). Statistical comparisons will use similar methodology as described in Section 6.10.1.

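### A COVID-19 case whose only positive RT-PCR is a hospital test cannot enter the primary or moderate-or-worse endpoint as the plan is written

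*SAP*

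**What the plan says.** **Endpoint.** SAP 6.10.1: "The endpoint for the primary analysis is defined as the first occurrence of COVID-19, defined as the detection of SARS-CoV-2 by reverse transcription", combined with mild or worse severity within 21 days. SAP 6.10.3.1 has the same structure for moderate or worse. No laboratory is named. Protocol 4.1.2 introduces the Table 1 severity grades for participants who are "SARS-CoV-2 positive as determined by standard RT-PCR assay or equivalent test".

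**Data capture.** In Protocol 1.3.1 the post-baseline nasal swab row gives central reading and adds "No samples needed if participant is hospitalized". The asterisk on that row leads to a footnote with two parts: the schedule resumes on discharge, and local laboratory results are not entered in the eCRF during the hospital stay. Clinical status in hospital is recorded daily, and for it "Documentation from hospital records is acceptable".

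**Missing data.** SAP 6.3.1: "participants in the Prevention population with zero post-baseline RT-PCR test results will be excluded". For those with at least one result, SAP 6.3.2 says that a participant who "is missing data used to determine COVID-19 status, the participant will be treated as not experiencing COVID-19", and it applies the same logic to moderate-or-worse disease. Neither section makes an exception for COVID-19 hospitalization or death.

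**The concern.** The definitions would admit a hospital RT-PCR, but the data collection keeps it out. For a hospitalized participant the plan collects the severity half of the endpoint and bars the detection half. The missing-data rules then turn the absent result into absence of disease, or remove the participant.

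At stake is the classification of some of the most severe cases in the trial. A fatal case confirmed only in hospital could be a non-case in the confirmatory analyses and a case in the analyses of COVID-19 hospitalization or death (6.10.3.4), deterioration (6.10.3.5) and COVID-19 mortality (6.10.3.6). The confirmatory and supportive results would then disagree about the same person. Moderate-or-worse cases also trigger the primary database lock in both Parts (SAP 6.1.5).

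**Working it through.** **Step 1: who is affected.** The rules, applied to a participant hospitalized with COVID-19:

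| Study swabs | Result under the plan |
|---|---|
| Positive before admission | Detected |
| Positive after discharge, by Day 57 | Detected |
| At least one post-baseline result, none positive | Non-event (6.3.1, 6.3.2) |
| No post-baseline result | Excluded (6.3.1) |

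Only the last two rows are the problem. A participant who dies in hospital has no swab after discharge, so a positive swab before admission is the only way in.

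**Step 2: whether another analysis settles it.**
- The supplementary analysis in 6.3.1 concerns the infection endpoint: "If a participant has a missing SARS-CoV-2 Infection Status due to death, study discontinuation, or the triggering of the Primary Database Lock", the participant is negative, with a weight equal to the share of the period to Day 29 completed. The death is down-weighted but still negative.
- The supplementary analysis in 6.3.2 covers missing status or "disease severity due to death unrelated to COVID-19, study discontinuation, or the triggering of the Primary Database Lock". This suggests that COVID-19 deaths were not meant to be treated as missing, but no rule says how to classify them.
- The death-or-positive sensitivity analysis in 6.10.3.2 covers Day 29 infection only.
- Adverse-event forms are no reliable backup. Protocol 10.3.1 leaves expected COVID-19 progression out of AE reporting unless it is more severe than expected.

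**Step 3: the plan's own figure.** Inputs from SAP 5.2 for Part 1: two-sided 0.05, 90% power, risk ratio 0.33, 33 events, about 1300 participants, 4.0% moderate-or-worse on placebo. Allocation is 1:1 (Protocol 6.3). Schoenfeld's formula gives (1.960 + 1.282)² / (0.25 × (ln 0.33)²) = 34.2 events. Power at 33 events is 89%. The stated 33 is close enough and is not in dispute.

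**Step 4: effect of one uncounted case, moderate-or-worse, Part 1.** With 1300 / 2 = 650 per arm:
- placebo: 650 × 0.04 = 26 events
- active: 650 × 0.04 × 0.33 = 8.58 events (total 34.58)
- one placebo case uncounted: 8.58 / 25 = 0.343
- one active case uncounted: 7.58 / 26 = 0.292

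The mean risk is (0.04 + 0.0132) / 2 = 0.0266. Replacing one uncounted case therefore takes about 1 / 0.0266 = 38 more participants.

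**Step 5: the primary endpoint.** The documents give no placebo rate for mild-or-worse COVID-19. I assume 6% to 12%, with risk ratio 0.33 and 650 per arm.

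| Assumed placebo rate | Events, placebo / active | One placebo case uncounted | One active case uncounted |
|---|---|---|---|
| 6% | 39 / 12.87 | 12.87 / 38 = 0.339 | 11.87 / 39 = 0.304 |
| 12% | 78 / 25.74 | 25.74 / 77 = 0.334 | 24.74 / 78 = 0.317 |

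**The case against.** **Most hospital cases will still be found.** Swabs are weekly and resume at discharge, so a reader should not infer that every case first confirmed in hospital is lost. That stands, and the point is limited accordingly. Discharge swabs protect the moderate-or-worse endpoint less well, however. SAP 4.1 counts severity in the 21 days after detection, so severity that peaked in hospital may fall before the counted date.

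**Hospital records might supply the result.** The visit-type table in Protocol 4.1.2 provides for virtual record collection in hospital, and the same section calls for retrieval of records. But retrieval follows the SoA, and the SoA footnote bars local results. This does not close the gap.

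**SAP 6.3.2 is not the source.** This stands in part. The block comes from the SoA footnote together with 6.3.1 and 6.3.2, so amending 6.3.2 alone would not help.

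**The events are reported elsewhere.** They are, in 6.10.3.4 to 6.10.3.6 and in all-cause mortality (6.16.2.6). Those analyses lie outside the tested primary and key secondary endpoints.

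**It does not cost power.** One might infer a shortfall, since two uncounted cases take the expected 34.58 to 32.58, below 33. The documents do not support that. The lock is triggered by counted cases, 1300 is an approximate average, and the Poisson standard deviation of 34.58 is about 5.9. The likely effect is delay or more enrolment. Part 1 limits this with an alternative trigger of 36 infections within 4 weeks, although only the primary endpoint is then evaluated. Part 2 has no alternative trigger.

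**Conclusion.** The point holds for a participant whose only positive RT-PCR is a hospital test. The written rules score that participant as a non-event, or exclude the participant if there is no post-baseline study result. This is a stated rule that gives the wrong classification, rather than a missing detail.

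The size is modest. One case moves the planned Part 1 moderate-or-worse risk ratio from 0.33 to 0.34 or 0.29. The primary moves to between 0.304 and 0.339 under the assumed 6% to 12% placebo rates. These figures rest on the plan's own rates and show single cases only.

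The documents do not give the number of such cases. It is probably small, because swabbing is weekly and resumes at discharge, and moderate disease need not lead to admission. A reader might infer that the result is biased in a particular direction. The documents do not support that either, since the direction depends on which arm loses cases. The reason to act is that the uncounted events would be among the most severe, and the repair is cheap.

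**What to change.** 1. Amend the SoA footnote in Protocol 1.3.1 so that the date and result of any hospital SARS-CoV-2 RT-PCR are recorded in the eCRF. State in SAP 6.3.1, 6.3.2 and 6.10.1 that a positive result within the endpoint time frame counts as detection and as a post-baseline result. Reconcile this with SAP 6.1.3, which ties the infection endpoints to visits within their window; a hospital test belongs to no study visit. Apply the change to the main analysis only for a Part that is still blinded. Otherwise run it as a sensitivity analysis. The current blinding status of Part 1 cannot be determined from the documents.
2. Add a sensitivity analysis of the primary and moderate-or-worse endpoints that counts COVID-19 hospitalization or COVID-19 death by Day 57 as an event even without a study RT-PCR result, and that keeps participants with no post-baseline swab who had such an event.

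**Cost.** A minor protocol amendment, one eCRF entry for date and result, SAP wording and one extra analysis. No visit or swab is added. The downsides are that local assays vary, results for past admissions must be retrieved from hospital records, and the second analysis relies on attribution to COVID-19 rather than laboratory confirmation. For that reason it belongs beside the main analysis and should not replace it.

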### ***6.3.3. Non-Responder Imputation (NRI)***

For analysis of other categorical efficacy, missing data will be imputed using a NRI method. Patients will be considered nonresponders for the NRI analysis if they do not meet the categorical efficacy criteria or have missing clinical efficacy data at a time point of interest.

In addition, patients who were not adequately assessed to determine if they meet the clinical requirements for response at the time point of interest are also considered to have failed treatment.

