Clinical status and concomitant procedures of special interest in hospitalized participants		Daily		X	X		Documentation from hospital records is acceptable. Includes: consciousness status (ACVPU), limitation on activities due to COVID-19, and requirements for 
Ongoing hospital medical careSupplemental oxygennon-invasive ventilation or a high flow oxygen devicemechanical ventilationextracorporeal membrane oxygenation, oradditional organ support (e.g. pressors, renal replacement)
SARS-CoV-2 Serology		X		X	X	X	Day 1: pre-dose. assessed at a central laboratory
Documentation of positive SARS-CoV-2 viral infection	X						Applies to participants in Part 3 only. Sample for first positive test must be collected within 10 days prior to start of infusion. Local laboratory and/or Point-of-Care testing.

Procedures	Screening	Evaluation Period			ETV	Post-treatment follow-up	Comments
Study Day	Max 7 day window	1	8	29		85	
Visit window (\pm number of days)	--	--	1	2		7	
SARS-CoV-2 nasopharyngeal swab taken from both nostrils		X	X	X	X	X	Day 1: pre-dose. assessed at a central laboratory No samples needed if participant is hospitalized.*
Urine pregnancy	X	X			X	X	Only for WOCBP (Section 10.4, Appendix 4) Local laboratory. Test performed in the 24 hours prior to study entry will be accepted for determination of eligibility. No samples needed if participant is hospitalized.*
Hematology		X		X	X	X	Day 1: pre-dose. Assayed by Lilly-designated laboratory No samples needed if participant is hospitalized.*
Clinical Chemistry		X		X	X	X	Day 1: pre-dose. Assayed by Lilly-designated laboratory No samples needed if participant is hospitalized.*

 • C-reactive protein; high-sensitivity • Ferritin • D-dimer • Procalcitonin • Troponin 		X		X	X		Day 1: pre-dose. Assayed by Lilly-designated laboratory No samples needed if participant is hospitalized.*
PK sample		X		X	X	X	Day 1: post-dose only (approx. 30 minutes after end of infusion) Assayed by Lilly-designated laboratory No samples needed if participant is hospitalized.*
Immunogenicity (ADA) sample		X		X	X	X	Day 1: pre-dose. Remaining days: Collect with time-matched PK sample. No samples needed if participant is hospitalized.*

Procedures	Screening	Evaluation Period			ETV	Post-treatment follow-up	Comments
Study Day	Max 7 day window	1	8	29		85	
Visit window (± number of days)	--	--	1	2		7	

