4.1.2. Evaluation Period

The evaluation period begins when the participant completes screening and is enrolled in the study. Assessments and procedures will be conducted as described in the SoA (Section [1.3](#)).

Participants in Part 1 will be randomized to placebo or LY3819253. The Sponsor will decide when to trigger activation of Part 2. Activation of Part 2 will be communicated to sites.

Participants in Part 2 will be assigned to a cohort as follows:

- Prevention Cohort: Participants who are SARS-CoV-2 negative during screening on the POC test will be randomized to one of three arms: placebo, LY3819253 700 mg, or LY3819253 350 mg + LY3832479 700 mg.
If enrolling to a placebo-controlled trial is challenged by an effective medication becoming available for prevention of COVID-19 and SARS-CoV-2, then the placebo arm may be dropped.

Note: It is possible that some participants have SARS-CoV-2 negative result on the screening point of care test, but could be positive on the baseline SARS-CoV-2 PCR test. The results from the baseline test will not be available until after the participant is randomized. Once positive results are known from the baseline test, these participants will be unblinded and have the option to continue to be followed for safety according to the Prevention Cohort SoA. Unblinded participants will not be included as part of the defined prevention population

The evaluation period for the Prevention Cohort is 8 weeks, with follow-up to Day 169.

- Treatment Cohort: Participants who test SARS-CoV-2 positive during screening with the POC test will be randomized to one of two arms: LY3819253 700 mg, or LY3819253 700 mg + LY3832479 1400 mg.

The evaluation period for the Treatment Cohort is 4 weeks, with follow-up to Day 85.

Participants in Part 3 will be randomized to LY3819253 700 mg or LY3819253 700 mg and LY3832479 1400 mg. The evaluation period for Part 3 is 4 weeks, with follow-up to Day 85. The Sponsor will decide when to trigger activation of Part 3. Activation of Part 3 will be communicated to sites. Part 3 may be activated prior to Part 2.

Part 2 and Part 3 could be activated concurrently. However, Part 3 will not enroll concurrently with Part 2 at the same facility.

Participants will receive one intravenous infusion of study intervention.

The maximum total duration of study participation for each participant of the prevention groups is 24 weeks. See the SOA for prevention groups in Section 1.3.1.

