#### **6.3.6. *Highest Disease States Imputation (HDSI)***

For the analyses related to National Institute of Allergy and Infectious Diseases (NIAID) ordinal scale, the following imputation will be considered if applicable.

For patients whose data is missing during the hospitalization period (not yet recovered), a score of 2, which is the worst value for a hospitalization status, will be used for imputation.

For patients whose data is missing after recovery or discharged, a score of 7, the worst value for a recovery or nonhospitalized status, will be used for imputation.

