#### **6.10.3.4. Hospitalization or Death Due to COVID-19 by Day 57**

The proportion of patients who experience hospitalization or death due to COVID-19 during the Evaluation Period will be summarized for participants in the Prevention population. In addition, the number of patients that experience hospitalization or death due to COVID-19 will be analyzed using logistic regression to compare each study intervention versus placebo, if there are sufficient data available. Statistical comparisons will be done using a logistic regression model. The model will include treatment, facility, role within the facility (resident vs staff) and sex as fixed effects. Missing data will be imputed using the NRI method as described in Section 6.3.3.

A listing of hospitalization status during the Evaluation Period will be created.

As an exploratory analysis, this analysis will be repeated on participants in the Treatment populations. Additionally, at each End of Evaluation Database Lock, the number of patients who are hospitalized or have died due to COVID-19 anytime after randomization will be analyzed to compare each study intervention versus placebo in the Prevention and Treatment populations, if there are sufficient data available.

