#### 6.16.2.2. Clinical Worsening based on the NIAID Scale

Clinical worsening is defined as the proportion (percentage) of participants with any worsening on the NIAID ordinal scale from baseline to the end of the Evaluation Period. Treatment group comparisons will be analyzed using logistic regression, if there are sufficient data available.

Missing data will be imputed using the NRI method as described in Section 6.3.3.

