#### **6.16.2.5. Proportions of Patients Hospitalized, Admitted to the ICU, Requiring Mechanical Ventilation**

The proportion of patients hospitalized, admitted to the ICU, requiring mechanical ventilation (oxygen source = “Intubation/Mechanical Ventilation”) will be evaluated separately using a logistic regression analysis with treatment, facility, and randomization stratification in the model. Missing data will be imputed using the NRI method as described in Section 6.3.3. These endpoints will be evaluated for the Prevention and Treatment populations at Day 57.

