#### 6.16.2.7. Persistently High Viral Load

In Part 3 (and only for Part 3), for any sample with a positive CoV-2 test result, an additional normalization step will be taken in the calculation of viral load. The viral load Ct value described in the previous steps will be subtracted by (RP Ct – 26.17), where RP Ct is a measure for the amount of material in the sample, and 26.17 is a historical average value of RP Ct for this assay, used here to center the RP Ct values. The log base 10 viral load will then be calculated from the result as above.

The proportion of patients with Day 7 viral load greater than 5.27 will be summarized by treatment for participants in the Part 3 Treatment population. Additionally, the proportion of patients with Day 7 viral load greater than 5.27 may be analyzed using logistic regression to compare treatment groups, if there are sufficient data available. Missing data will be imputed using the NRI method as described in Section 6.3.3.

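### SAP 6.3.3 non-responder imputation is worded for favourable responses, but six of the seven analyses that cite it count unfavourable events, so in its natural sense missing data become events

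*SAP*

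**What the plan says.** SAP 6.3.3 covers categorical efficacy endpoints other than the primary and key secondary ones. A patient who does not meet the efficacy criteria, or whose data are missing, is a nonresponder. Patients not adequately assessed for response "at the time point of interest are also considered to have failed treatment".

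Seven analyses invoke it with one sentence, "Missing data will be imputed using the NRI method as described in Section 6.3.3", and add no event coding:

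| SAP section | What is counted | Direction |
|---|---|---|
| 6.10.3.4 | COVID-19 hospitalization or death | unfavourable |
| 6.10.3.5 | COVID-19-related deterioration | unfavourable |
| 6.10.3.6 | COVID-19 death | unfavourable |
| 6.16.1.3 | SARS-CoV-2 clearance | favourable |
| 6.16.2.2 | "participants with any worsening on the NIAID ordinal scale from baseline to the end of the Evaluation Period" | unfavourable |
| 6.16.2.5 | hospitalization, ICU, mechanical ventilation | unfavourable |
| 6.16.2.7 | "The proportion of patients with Day 7 viral load greater than 5.27 will be summarized by treatment" | unfavourable |

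For the primary and key secondary endpoints, SAP 6.3.1 and 6.3.2 say explicitly that a participant with at least one post-baseline RT-PCR result and otherwise missing data did not have the event. They add a supplementary analysis weighted by the proportion of the Evaluation Period completed.

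**The concern.** The rule's vocabulary (nonresponder, response, failure) assumes that meeting the criteria is good. Where the endpoint is a harm, it can be applied in two ways:

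- **Natural sense.** Missing means failed treatment, so missing becomes the event. A participant with one negative swab who then drops out would count as free of COVID-19 in the primary analysis but as hospitalized or dead from it in 6.10.3.4.
- **Literal substitution.** If the endpoint itself is taken as the criteria, missing means the criteria were not met, so missing becomes no event. This agrees with 6.3.1 and 6.3.2 but sits badly with the failed-treatment wording.

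Two programmers could therefore report different counts and odds ratios for three named Part 1 secondary endpoints (6.10.3.4 to 6.10.3.6) and for the exploratory ones. Under the natural reading, when events are rare, imputed events can outnumber real ones. Equal missingness pulls the odds ratio toward 1, and unequal missingness can produce an effect where none exists.

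**Working it through.** The documents give no figure for missing data and no event rate for any of these endpoints, so this is an illustration.

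**Inputs**
- n = 650 per arm: about 1300 Part 1 Prevention participants (SAP 5.2), randomized 1:1 (Protocol 6.3).
- Risk ratio 0.33 and 4.0% placebo risk: Part 1 planning values (SAP 5.2). The 4.0% is for moderate or worse COVID-19 and the risk ratio for the primary and key secondary endpoints; both are borrowed here. They give 650 × 0.04 × 1.33 = 34.6 expected events, close to the plan's 33.
- Placebo risks of 1% and 2%: assumed.
- Missing proportion m: assumed, and unrelated to event risk.

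**Formulas**, for true risk p in an arm
- Missing = event: observed risk = m + (1 − m)p.
- Missing = no event: observed risk = (1 − m)p.
- Odds ratios are unadjusted; the SAP model for the secondary endpoints also includes facility, role and sex.

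**Equal missingness, example** (p = 0.02 and 0.0066, m = 0.01)
- Placebo: 0.01 + 0.99 × 0.02 = 0.0298.
- Active: 0.01 + 0.99 × 0.0066 = 0.0165.
- Odds ratio 0.55. Imputed events: 1300 × 0.01 = 13, against 650 × (0.02 + 0.0066) = 17.3 true events.

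Odds ratio when missing = event:

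| Placebo risk | none missing | 0.5% | 1% | 2% | 3% | m at which imputed = true events |
|---|---|---|---|---|---|---|
| 1% | 0.33 | 0.55 | 0.66 | 0.77 | 0.83 | 0.7% |
| 2% | 0.33 | 0.46 | 0.55 | 0.66 | 0.73 | 1.3% |
| 4.0% | 0.32 | 0.39 | 0.45 | 0.54 | 0.61 | 2.7% |

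The last column solves 1300m = 650 × 1.33p, so m = 1.33p/2. Under missing = no event the odds ratio stays at 0.32 to 0.33 throughout.

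**Unequal missingness, no true effect** (p = 0.02 in both arms; m = 0.02 placebo, 0.01 active)
- Missing = event: 0.0396 versus 0.0298, odds ratio 0.75 (0.66 at 1% risk, 0.83 at 4%).
- Missing = no event: 0.0196 versus 0.0198, odds ratio 1.01.

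**Two endpoints need separate treatment**
- NIAID worsening (6.16.2.2) cites NRI, but SAP 6.3.6 has its own rule for NIAID analyses: "For patients whose data is missing after recovery or discharged, a score of 7". On the Appendix 1 scale, an imputed 7 is worsening from a baseline of 8 but not from 7. Missing = event therefore differs from 6.3.6 at baseline 7.
- For viral load (6.16.2.7, Part 3 only), the Protocol 1.3.2 swab row says "No samples needed if participant is hospitalized". Under literal substitution, a participant unsampled because hospitalized counts as not having high viral load.

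**The case against.** The strongest reply is that the direction is fairly clear: for a harm, failed treatment can only mean the event, and this is a conservative choice lacking one clarifying line. That is largely right about the direction. It does not explain why the SAP should impute COVID-19 hospitalizations and deaths when its primary rule does the opposite.

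The second reply is that little would be missing, and much of it stands. SAP Table 6.2 ends the Evaluation Period at discontinuation, which limits missingness for 6.10.3.4 (despite its Day 57 heading) and 6.16.2.2. SAP 6.1.3 makes by-Day-57 endpoints cumulative. Hospitalization events are dated (Protocol 8.2.4), hospital records are sought (Protocol 4.1.2), vital status is searched (Protocol 7.3), and discontinuation is expected to be uncommon (Protocol 7.2). Death is least exposed. Even so, the table shows that 1% missing is enough to matter.

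A reader might also infer three stronger points that the documents do not support:
- **Infection by Day 57 (6.10.3.3) falls under NRI by default.** It names no missing-data rule, but it uses the 6.10.1 model, so following the primary analysis's handling is equally plausible.
- **Day 57 status is undefined in Part 2 Treatment and Part 3.** SAP 6.16.2.5 says "These endpoints will be evaluated for the Prevention and Treatment populations at Day 57", while Protocol 4.1.2 says "The evaluation period for the Treatment Cohort is 4 weeks, with follow-up to Day 85" and gives Part 3 the same schedule. But hospitalization events are also recorded at Day 85, and hospitalization and ICU dates are collected, so Day 57 status can be derived for those. This is a time-point mismatch only.
- **Everyone unfinished at the Primary Database Lock becomes an event.** SAP 6.3.3 does not say that data not yet due are missing. Lock-related missingness is named only in 6.3.1 and 6.3.2, for other endpoints. If it were read that way, with an assumed 5%, 10% or 20% unfinished, the 2% case would give 0.80, 0.89 or 0.94, at that lock only.

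**Conclusion.** The point holds. A rule written for favourable responses is applied to six unfavourable endpoints; in its natural sense it codes missing data as harm, contrary to the SAP's own primary rule, and no citing section settles the direction. The size depends on assumed missing and event rates: an odds ratio of 0.55 instead of 0.33 at 2% placebo risk with 1% missing, or 0.75 with no true effect and 2% versus 1% missing.

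The reach is limited. A reader might infer that the main efficacy conclusions are at risk; they are not, because the primary and key secondary endpoints have their own rule. The affected analyses are other secondary or exploratory, outside the multiplicity scheme (SAP 6.5), mostly conditional on sufficient data, and re-run at the End of Evaluation lock (SAP 6.1.5). Severity is minor to should-fix.

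**What to change.** - **6.10.3.4 to 6.10.3.6 and 6.16.2.5:** replace the NRI sentence with a rule that no recorded event counts as no event, derived from event dates. Add the follow-up-weighted supplementary analysis of 6.3.1/6.3.2, which also handles participants unfinished at the Primary Database Lock. Keep missing = event as a sensitivity analysis.
- **6.16.1.3 (clearance):** keep NRI as written.
- **6.16.2.2:** name one rule, either NRI with its direction stated or the 6.3.6 rule.
- **6.16.2.7:** state the coding direction and report the number missing by arm.
- **Minor clarifications:** state that 6.10.3.3 follows 6.3.1, and align the Day 57 time point in 6.16.2.5 with the 4-week evaluation period of Part 2 Treatment and Part 3.

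The cost is SAP wording only, with no new data. The downside is that counting no recorded event as no event can understate event rates if missingness is informative; the sensitivity analysis shows by how much.
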